### 3. Vulnerable Populations

- Children, fetuses, neonates, or prisoners are not included in this research study.

### 4. Populations vulnerable to undue influence or coercion

Should an OSU employee or student (or their surrogate) be approached for enrollment, they will be given the opportunity and time to consider participation and will be reassured that declining to participate will not jeopardize or hinder their standard of care at the OSU Wexner Medical Center, nor will it have any bearing on either their student status or employment.

### e) Inclusion of Women and Minorities

Both men and women of all races and ethnic groups are eligible for this study.

## **C. Study Plan**

This is a preliminary single-arm study. The study will last up to 6 weeks including the screening period. Subjects will receive active tDCS for 30 minutes before their scheduled work hours at least 3x/week for two consecutive weeks.

Outcome measures will include: psychomotor vigilance test (PVT) and the Karolinska Sleepiness Scale (KSS) which will be obtained during the shift work.

## **Visit Schedule**

### **A) Screening visit**

During this visit, the following will be obtained for all subjects:

- a. Screening Informed consent (if not obtained on a prior separate visit)
- b. Evaluation for SWD by investigator
- c. Pregnancy test, if applicable
- d. Height and weight
- e. Blood pressure and pulse rate
- f. Medication list
- g. Cognitive Tasks results
- h. Epworth sleepiness scale (ESS)
- i. CPAP compliance for those who are known to have sleep apnea
- j. MNC score
- k. HSAT, if applicable as explained above
- l. Expected visit length: 60 minutes**

The following are the reasons why subjects may not proceed with the study after screening:

- a) If they are determined to have significant sleep apnea, this will end their participation in this research study. The home sleep study results will be provided to research participants or their health care provider for referral for appropriate treatment.
- b) The investigators determine that the subject does not have shift work sleep disorder.

Those who remain eligible will then sign a separate informed consent for the remainder of the study. They will be requested to complete a baseline PVT and KSS during their shift work prior to the tDCS stimulation sessions. The PVT is a test that measures the speed with which subjects respond to a visual stimulus. It is a simple task where the subject presses a button as soon as the light appears. The light will turn on randomly every few seconds for 3 minutes. The KSS is a subjective measure of sleepiness. They will be provided with a mini-IPAD that contains the PVT and KSS apps. The PVT and KSS will only take 4 minutes and will be collected around 6 pm, 12 midnight and 4 am.

**B) Visit 1** (stimulation #1)

During this visit, the following will be obtained for all subjects:

- a. Study Informed consent (if not already obtained)
- b. Resting blood pressure and pulse rate
- c. Changes to Medication

They will then receive active tDCS for 30 mins. PVT **during** the active tDCS

- d. Side effects questionnaire **after** the active tDCS
- e. Actigraphy equipment will be provided to be worn throughout the duration of the study. Instructions on how to wear an actigraph device around their wrist that measures both the rest-activity cycle will be provided.
- f. **Expected visit length: 60 minutes**

**C) Visit 2** (stimulation #2)

During this visit, the following will be obtained for all subjects:

- a. Resting blood pressure and pulse rate
- b. Changes to Medication

They will then receive active tDCS for 30 mins. PVT **during** the active tDCS

- a. Side effects questionnaire **after** the active tDCS
- b. **Expected visit length: 60 minutes**

**D) Visit 3** (stimulation #3)

During this visit, the following will be obtained for all subjects:

- a. Resting blood pressure and pulse rate
- b. Changes to Medication

They will then receive active tDCS for 30 mins. PVT **during** the active tDCS.

- c. Side effects questionnaire after the active tDCS
- c. PVT and KSS (6 pm, 12MN, and 4 am)
- g. **Expected visit length: 60 minutes**

**Visits 1-3 will occur during a one week period. Subjects will then be asked to obtain the KSS score and PVT during their shift work at 6 pm, 12 MN, and 4 am at the end of Visit 3.**

E) Visits 4, 5, 6 represent the second week of tCDS active stimulation and will be similar to Visits 1-3 with an expected visit length of 60 minutes per visit and will occur over a one-week period.

Subjects will be asked to obtain the KSS score and PVT during their shift work at 6 pm, 12 MN, and 4 am at the end of Visit 6. In addition, at the end of Visit 6, the following will be obtained **after** the active tDCS

- i. Cognitive Tasks results
- ii. Epworth sleepiness scale (ESS)

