#### **B. Subject Selection:**

##### 1. Inclusion/Exclusion Criteria

###### *A. Key Inclusion Criteria*

- age 18-65 years
- works 5 or more night shifts per month (each shift lasting at least 10 hours, with  $\geq 6$  hours worked between 10 pm and 8 am) with plans to maintain this schedule for the duration of the 3-week trial
- meets the criteria for SWD according to the International Classification of Sleep Disorders and evaluation of a sleep medicine provider (physician or nurse practitioner) during a screening evaluation:

a) affirmative answers to Do you experience excessive sleepiness? (yes/no); “Do you experience difficulties with falling asleep during opportunities for sleep? (yes/no); “Is the sleep or sleepiness problem related to a work schedule where you

have to work when you would normally sleep? (yes/no)”; and “Has this sleep or sleepiness problem related to your work schedule persisted for at least three months? (yes/no)

b) based on the evaluation of the sleep medicine provider, the sleep and/or wake disturbance are not better explained by another current sleep disorder, medical or neurologic disorder, mental disorder, medication use, poor sleep hygiene, or substance abuse disorder.

- Stable medication dosage over previous 4 weeks.
- Able to understand English and give a written informed consent document.

*B. Key Exclusion Criteria*

- Currently taking stimulant medications such as Modafinil, Armodafinil, Methylphenidate, or Dextroamphetamine.
- History of automobile accident due to falling asleep while driving
- Inability to understand or read English
- Self-reported Substance abuse (current)
- Excessive alcohol consumption defined as:
  - More than 3 glasses of wine a day
  - More than 3 beers a day
  - More than 60 mL of hard liquor a day
- Presence of cardiac pacemaker or automatic implantable cardioverter-defibrillator (AICD).
- Pregnancy, lactation (will be screened with urine pregnancy test)
- Non-removable metal or tattoos around head
- Use of implantable birth control device such as Implanon
- History of frequent severe headaches
- Unstable coronary artery disease
- Uncontrolled Seizure disorder
- Uncontrolled hypertension
- Any other clinically significant condition that, in the opinion of the Investigator, might put the subject at risk of harm during the study or might adversely affect the interpretation of the study data.

*b) Screening Procedures*

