### f) **Questionnaires**

The following questionnaires will be completed by the subjects:

- a. Karolinska Sleepiness Scale (KSS). Values will be collected prior to their shift work (around 6pm) and during shift work (around 12 midnight and around 4 am). These data will be obtained prior to tDCS stimulation, after the third stimulation and after the 6th stimulation sessions. They will be asked to rate how sleepy they are according to the following scale:
  9. Extremely sleepy, fighting sleep
  8. Sleepy, some effort to keep alert
  7. Sleepy, but no difficulty remaining awake
  6. Some signs of sleepiness
  5. Neither alert nor sleepy
  4. Rather alert
  3. Alert
  2. Very alert
  1. Extremely alert
- b. Epworth Sleepiness Scale Score (ESS) at baseline and after the 6th stimulation session.
- c. Side Effects

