#### IV. Data Analysis

##### *Sample size:*

The sample size is selected such that we have power to detect differences in the mean reciprocal reaction time (mean 1/RT) and KSS, which are our co-primary endpoints. Differences from baseline in the co-primary endpoints will be assessed at Visit 6.

We plan to enroll a total of 45 subjects. We assume a screen failure rate and a loss to follow up rate of 40%. Thus, we anticipate at least 27 evaluable subjects. Once 27 evaluable subjects have completed the study, enrollment will stop. We will control the type I error rate at 0.10 for assessing the primary endpoints conservatively using a Bonferroni correction. With this sample size, we have 80% power to detect an improvement of 0.50 standard deviations in mean 1/RT with an alpha level of 0.05 using a one-sided t-test. For the KSS, we assume a standard

deviation of  $2^9$  and have 80% power with this sample size to detect a reduction in KSS of 1 with an alpha level of 0.05 using a one-sided t-test.

Statistical Methods:

The primary analysis will examine the difference in KSS and mean 1/RT at 4 AM at Visit 6 and baseline. To analyze differences in KSS at Visit 6 and baseline, and differences in mean 1/RT at Visit 6 and baseline, we will use paired t-tests using the worst values during the shift work. We will use Holm's Method to account for multiple testing and control the familywise error rate.

Secondary analyses will include the mean inverse response time and additional outcomes from the PVT and subjective questionnaires. To analyze differences in the number of lapses at Visit 4, we will use a Poisson regression model to compare the lapse rate at Visit 6 to the baseline rate. Additional questionnaires (ESS) will be assessed using paired t-tests.

We will also build longitudinal models to fully explore changes in outcomes both across weeks and within shifts. We may also explore joint models of subjective and objective outcomes to better characterize correlation between outcomes and their changes over time. Characteristics of participants will be summarized by randomized treatment group using appropriate descriptive statistics. We will also summarize any reported side effects of treatment. Additional exploratory analyses may be conducted at the discretion of the study team.

Interim Analysis:

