**V. Event Reporting**

(a) Adverse Events

The ICH Guideline for Good Clinical Practice E6(R1) defines an adverse event (AE) as:

Any untoward medical occurrence in a patient or clinical investigation subject administered a pharmaceutical product and which does not necessarily have a causal relationship with this treatment. An AE can therefore be any unfavorable and unintended sign (including an abnormal laboratory finding), symptom, or disease temporally associated with the use of a medicinal product, whether or not considered related to the medicinal product.

As this is a study that does not include a pharmaceutical product intervention, this definition would include AEs that occur as a result of protocol procedures and protocol treatment.

A serious adverse event (SAE) is any AE that:

- Results in death
- Is immediately life-threatening

This term refers to an event in which the subject was at risk of death at the time of the event; it does not refer to an event that may have led to death.

- Requires inpatient hospitalization or prolongation of existing hospitalization  
In general, hospitalization signifies that the subject has been detained (usually involving at least an overnight stay) at the hospital or emergency ward for observation and/or treatment that would not have been appropriate in an outpatient setting.
- Results in persistent or significant disability/incapacity  
The term disability means a substantial disruption of a person's ability to conduct normal life functions.
- Is an important medical event that may jeopardize the subject or may require medical intervention to prevent one of the outcomes listed above.

Medical or scientific judgment should be exercised in deciding whether expedited reporting is appropriate in this situation. Examples of medically important events are intensive treatment in an emergency room or at home for allergic bronchospasm, blood dyscrasias, or convulsions that do not result in hospitalizations; or development of drug dependency or drug abuse.

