#### 1. Collecting and reporting adverse events:

All AEs occurring after subject has signed consent and up to the study completion visit must be recorded on specific data collection forms.

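### The side-effects questionnaire has no pre-stimulation reading, so in this single-arm trial non-specific symptoms already present may be counted as side effects of tDCS

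*Combined protocol and SAP*

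**What the plan says.** In III.C Study Plan, the visit descriptions for Visits 1, 2 and 3 each list "Side effects questionnaire after the active tDCS". Visits 4 to 6 "will be similar to Visits 1-3 with an expected visit length of 60 minutes per visit", so the same order carries over. The schedule table marks side effects at Visits 1 to 6 and leaves the screening column empty.

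The Questionnaires section of Detailed Procedures treats the other scales differently. The KSS has a reading before stimulation, and the ESS line begins "Epworth Sleepiness Scale Score (ESS) at baseline and after the 6" (the sixth session). The side-effects item beside them has no timing and no content.

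On design, the Study Plan says "This is a preliminary single-arm study". On analysis, the Statistical Methods text in IV. Data Analysis says "We will also summarize any reported side effects of treatment" and adds no baseline comparison, treatment-emergent definition or attribution rule.

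There is also a separate adverse-event route. Event Reporting states: "All AEs occurring after subject has signed consent and up to the study completion visit must be recorded on specific data collection forms". It adds that "this definition would include AEs that occur as a result of protocol procedures and protocol treatment". The Data Safety Monitoring Plan has the study team assess adverse events one by one as they become known.

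**The concern.** A symptom reported after a session is informative about tDCS only if there is something to compare it with. A sham arm would give a between-group reference, and a pre-session reading would give a within-subject one. This plan has neither for the side-effects form.

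The population makes this more than a formality. Subjects are enrolled because they have excessive sleepiness and trouble sleeping around night work. The nearest symptom-specific exclusion is "History of frequent severe headaches", which leaves milder or less frequent headache eligible. Fatigue and poor concentration are also plausible background complaints.

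At stake is how far the side-effect table can be interpreted. A missing pre-session rating cannot be recovered once the session has been given.

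**Working it through.** No stated figure in the plan depends on this point, so the check is mainly a reading of the relevant sections side by side.

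1. **Is there any pre-stimulation administration?** The visit descriptions (after stimulation), the schedule table (Visits 1 to 6, not screening) and the Questionnaires section (no timing) agree that none is scheduled.
2. **Is there a concurrent control?** No; the trial has a single arm.
3. **Does the analysis supply a rule?** No; Statistical Methods summarises what is reported.
4. **Does adverse-event recording supply the baseline?** Only in part. It starts at consent, before the first stimulation, but it covers events that occur after consent. A symptom the subject already had at consent is not such an event, and the log is not a rating of the same items on the same form.

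**Illustration of scale.** The background prevalence p (share of visits at which a symptom is present regardless of tDCS) is assumed, because the documents give none. The number of evaluable subjects, 27, is the plan's: 45 × (1 − 0.40) = 27. With no tDCS effect, the proportion reporting the symptom at least once over six post-session forms is

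- fully persistent within subject: p
- independent between visits: 1 − (1 − p)^6

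| Assumed p | Persistent | Expected of 27 | Independent | Expected of 27 |
|---|---|---|---|---|
| 5% | 5% | 1.4 | 1 − 0.95^6 = 26% | 7.2 |
| 10% | 10% | 2.7 | 1 − 0.90^6 = 47% | 12.7 |
| 20% | 20% | 5.4 | 1 − 0.80^6 = 74% | 19.9 |

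Symptoms that subjects habitually carry are correlated within subject, so for those the persistent columns are the better guide.

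**What a single baseline would remove.** Suppose a symptom present at a visit is present both before and after that day's session. With a pre-stimulation form at Visit 1 only and a new-or-worse rule, persistent symptoms are removed entirely. Under independence between visits, a subject is still counted if free of the symptom at Visit 1 and affected at any of the five later visits: (1 − p) × [1 − (1 − p)^5]. At p = 10% this is 0.90 × (1 − 0.90^5) = 0.90 × 0.410 = 0.369, or 10.0 of 27, against 12.7 without a baseline. A form before each session would remove these as well.

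**The case against.** The strongest reply is that the questionnaire is not the only safety source. Adverse events are recorded from consent onward and assessed individually, and the monitoring plan looks at reactions related to study procedures. This stands as mitigation. It does not close the gap, because judging relatedness is harder without a pre-session rating, and the plan gives no method for that judgement.

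Second, the form's content is not shown. It may ask about onset or relation to stimulation, and it may not include the non-specific items at issue. That is why the point says symptoms may be counted. Answers on onset would help, but they would rest on recall by subjects who know they received active stimulation.

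Third, the problem depends on the item. The Background section names mild scalp itch or tingle as the commonest side effect, and this is easy to attribute. There is also an investigator-judgement exclusion for conditions that could cloud the data. Both stand; the concern is confined to non-specific symptoms.

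Fourth, counting background symptoms would mostly overstate harm, which is the cautious direction, and only a descriptive table is affected. This also stands and keeps the grade low.

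A reader might go further and infer three things that the documents do not support:

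- **Delayed effects are captured only after the next session.** This is true of the questionnaire alone. Under Event Reporting, a next-day symptom is to be recorded as an adverse event.
- **The decision to stop for risk would rest on these questionnaire counts.** The Data Safety Monitoring Plan describes individual assessment of events.
- **Tolerability is the result meant to support the larger trial.** The Objectives section names sleepiness and vigilance, and describes an efficacy study.

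**Conclusion.** The point holds in a limited form. The side-effects questionnaire is given only after stimulation, there is no sham arm, and no new-or-worse rule is stated. Non-specific symptoms already present may therefore be counted as side effects of tDCS in the questionnaire data. It would be tempting to say that they *are* so counted. The documents do not support that, because they set no counting rule and do not show the form.

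The effect is confined to the descriptive side-effect summary. The co-primary endpoints, the sample size, power and type I error are untouched. The size cannot be derived from the documents; the illustrative range rests on assumed prevalences and on how strongly reports correlate within a subject. The conclusion also assumes that the form includes at least some non-specific items and does not itself establish a pre-session state. Grade: cheap improvement.

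**What to change.** 1. In III.C, give the same side-effects questionnaire before stimulation at Visit 1. Optionally give it before every session, when resting blood pressure is taken; this is the version that also handles symptoms that come and go between visits.
2. Add the pre-stimulation administration to the schedule table, and state the timing in the Questionnaires section.
3. In Statistical Methods, state that questionnaire side effects will be summarised by item as those new or worse than the pre-stimulation rating, alongside the raw post-session counts, so that nothing reported is hidden.

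The cost is an estimated one to two minutes per administration within the planned 60-minute visit, one table entry and a sentence or two of text, with no new staff or equipment. The change does not replace a control arm: symptoms that arise by chance or expectation during a session would still be counted.

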**Visit Schedule**

Procedures	Visit #						
	S	1	2	3	4	5	6
Screening consent	x						
Study consent		x					
Medication list	x	x	x	x	x	x	x
Height and weight	x						
BP and Pulse rate	x	x	x	x	x	x	x
MNC	x						
HSAT, if applicable	x						
Pregnancy test, if applicable	x						
Cognitive tasks	x						x
ESS	x						x
Actigraphy		x	x	x	x	x	x
tDCS		x	x	x	x	x	x
Side-effects		x	x	x	x	x	x
*PVT		x		x			x
*KSS		x		x			x

\*obtained during the subjects' shift work at baseline at baseline prior to stimulation and after every 3 tdcS stimulation session

S= screening visit (requires a separate consent)

BP= blood pressure

MNC= modified neck circumference

HSAT= home sleep apnea test

tDCS= transcranial direct current stimulation

PVT= psychomotor vigilance test

KSS= Karolinska sleepiness scale

ESS= Epworth Sleepiness Scale

## Detailed Procedures

### a) **Medication List**

For all subjects we will obtain information about their medications or any changes to their medications.

### b) **Height and Weight**

Weight and height measurements (to calculate BMI) will be done without shoes.

### c) **Blood Pressure**

The standard operating procedure for obtaining sitting blood pressure will be followed.

**Medical Alert Procedure.** Subjects in these protocols may be identified to have clinical abnormalities that require medical attention. Research staff would notify [name] or a physician co-investigator immediately for Systolic BP >200 mmHg or diastolic BP >120 mmHg.

### d) **Modified Neck Circumference (MNC) score**

This will be obtained during the screening visit. The MNC is calculated as the neck circumference measured in centimeters and adjusted if the patient has hypertension (4 cm is added), is a habitual snorer (3 cm is added), or is reported to choke or gasp most nights (3 cm is added).

### e) **Home sleep apnea testing (HSAT)**

This is part of the screening procedure. Subjects with an MNC score >43 cm high, indicating a moderate to high probability of having obstructive sleep apnea (OSA), will have home sleep apnea testing (HSAT). Those with an apnea-hypopnea index of  $\geq 15$ /hour based on the HSAT will be excluded and referred to their primary care physician or the sleep medicine clinic for treatment discussion. Subjects will be given a copy of the HSAT report. Subjects will be given instructions on how to use the HSAT equipment which is used routinely in clinical practice for home sleep apnea testing by clinical staff of the OSU Lung Center. The device will be preset to turn on automatically at home at the desired time. HSAT includes recordings of nasal pressure, thorax and abdominal movements, oxyhemoglobin saturation, and pulse rate. Subjects will be provided a telephone number to call should they have any questions about the device.

HSAT will be scored according to standard criteria. Briefly, an apnea is scored when all of the following criteria are met: a drop in airflow sensor excursion by > 90% of baseline, the duration of the event lasts at least 10 sec, and at least 90% of the event's duration meets the amplitude reduction criteria. An apnea is classified as obstructive if it is associated with continued or increased respiratory effort throughout the entire period of absent airflow, central if it is associated with absent respiratory effort throughout the entire period of absent airflow, and mixed if it is associated with absent respiratory effort in the initial portion of the event, followed by resumption of respiratory effort in the second portion of the event. A hypopnea is scored if the following criteria are met: the airflow signal excursion drops by >30% of baseline, there is a >4% desaturation from pre-event baseline, and at least 90% of the event's duration meets the amplitude reduction criteria.

